7.1 Primary Effectiveness Endpoint

The percentage of EBV Treatment arm study participants meeting the threshold of $\geq 15\%$ improved forced expiratory volume in one second (FEV_1), obtained immediately following

bronchodilator therapy, as compared to the percentage in the Control arm at 1 year post-procedure.

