20.3.1 Sample Size Rationale

The results of two prospective studies were used to inform the sample size estimation. The Endobronchial Valve for Emphysema Palliation Trial ("VENT Pivotal Trial", IDE#G020230, NCT00129584) was a multi-center, prospective, randomized, controlled study conducted at sites in both the United States and Europe to assess the safety and effectiveness of using the Zephyr EBV device for palliating symptoms associated with severe heterogeneous emphysema. Four hundred ninety two (492) participants were enrolled into the study and randomized to Zephyr EBV Treatment or medical management (control) [16,17]. The Chartis Pulmonary Assessment System study is a recently completed prospective post-market study that was conducted in Germany, The Netherlands, and Sweden. The primary objective of the study was to quantify the accuracy of the Chartis System when used to identify targeted treatment lobes as having or not having inter-lobar CV in patients with emphysema who were to be treated using endobronchial valves (26). The results of both the VENT Study and the Chartis System study showed that treatment effect with the endobronchial valve is correlated with lack of inter-lobar CV [16,17,25].

Patients in the VENT Study and in the Chartis Study who were considered to have little or no inter-lobar CV contributed the information used for the sample size estimate. Patients who have little or no lobar CV in the targeted treatment lobe are expected to be good responders to endobronchial valve treatment. For the sample

size estimate, a 'responder' was considered to be a study participant who had $\geq 15\%$ improved FEV₁ after EBV treatment.

Based on the results of these studies, the responder rate in the EBV Study Treatment Group is expected to be approximately 35% at 1 year. The responder rate for the control group is not expected to exceed 10% at 1 year. Assuming a two-sided 0.05 alpha level, study power of 90%, and 2:1 allocation random assignment, a sample size of 147 will be adequate to test for superiority.

The study sample size will be increased to 183 in order to allow for 20% lost to follow-up and incomplete data. Each study site will be allowed to enroll a maximum of 25 study participants.

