Means, standard deviations, medians, and confidence intervals will be reported for all continuous variables. Dichotomous variables will be reported as percentages and the numerator and denominator will be reported and defined.

II. Analyses of the Patient Populations

These analyses are intended to determine the similarity of two treatment groups and similarity of patients from different study sites with respect to important demographic or other variables, either known or suspected to have an influence on the outcome variables. The absence of similarity for any variable will identify that variable as a potential covariate in subsequent analyses.

- A. Comparability of Treatment Groups To assess the success of the randomization process, the demographic and prognostic variables measured at study entry will be compared between the Treatment and Control arms. Continuous variables will be compared with the two-sample t-test or the Wilcoxon two-sample rank test, and categorical variables will be compared with the Fisher's exact test or a Chi-square test. Comparability analyses will be done with two-sided tests with significance level of 0.05.
- B. Study Site Comparability –The appropriateness of pooling the data across study sites will be determined on a clinical basis, i.e., to ascertain if the sites used a common protocol, the sponsor adequately monitored the study to assure protocol compliance, and the data gathering and validation mechanisms were the same across all study sites (Meinert, 1986).

An analysis will be done to determine if the magnitude of the clinical effect of the primary outcome is maintained if sites and/or site by treatment interactions are included in an analysis of covariance model. We expect the majority of sites will show the treatment to be beneficial but statistically one would not expect all sites to show the treatment to be beneficial. For those sites with contrary results, an analysis will be attempted to determine what factors at those sites led to the result (See expert statistical testimony from Dispute Resolution Panel transcript September 6, 2001).

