A. Analysis of the Primary Effectiveness Endpoint

Both an interim and an end of study analysis for the primary effectiveness endpoint are planned. The primary effectiveness endpoint is the difference between the EBV treatment arm and control arm in percentage of study participants who reach a threshold of \geq 15% improved FEV₁, collected post-bronchodilator, at 1 year (see Table 1). The FEV₁ value will be calculated by determining the percentage change for FEV₁ from baseline to 1-year post-procedure using: ((FEV₁ at 1-year follow-up subtracted from FEV₁ at baseline) / (FEV₁ at baseline)) for individual study participants. The two arms will be compared using the standard normal Z-statistic.

Table 1. Primary Effectiveness Endpoint

Variable	Unit	Values Statistically Evaluated
Forced Expiratory Volume (FEV ₁)	>15% improved	percentage of participants

An interim data analysis designed to evaluate effectiveness for continuing crossover of control arm study participants at the 1-year follow-up to EBV treatment will be performed when 74 (50% of the total 147) study participants have completed the 1-year follow-up. The interim analysis will be reviewed by the DSMB.

To account for the interim analysis, the power spending function, defined as:

$$\alpha(t) = \alpha t^{\phi}$$

will be used to preserve an overall type I error rate of 0.05 for the study. Using the nTerim program (Statistical Solutions) to calculate the power spending function with: $\alpha = .05, \phi = 2.3 \text{ and } t = .5, \alpha(t) = .01,$

the value of the Z-statistic must exceed 2.571 (nominal alpha <0.01) for the null hypothesis to be rejected at this interim look (see Table 2).

 Table 2. Power Spending Function for Interim Analysis

Looks	1	2
Time	0.5	1
Lower Bound	-2.57057	-2.00360
Upper Bound	2.57057	2.00360
Nominal Alpha	0.01015	0.04511
Incremental Alpha	0.01015	0.03985
Cumulative Alpha	0.01015	0.0500
Exit Probability	38.75	50.52
Cumulative Exit Probability	38.75	89.28

If Z \geq 2.571 then continuing crossover of control arm study participants will be strongly justified since the p-value will be \leq 0.01. This observation may provide evidence to stop the trial early.

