The study hypothesis will be tested again at the end of the study. The Z-statistic will be calculated again, and by taking into account the interim analysis, will have a final critical boundary value of 2.004, per the nTerim program. If the trial is not stopped as a result of the interim analysis, then the final Z-statistic must be greater than or equal to 2.004 in order to reject the null hypothesis at the final analysis (at the overall 2-sided 5% significance level). Test statistic is "Z" as defined as:

$$Z = \frac{p_T - p_C}{\sqrt{p(1 - p)\left(\frac{1}{n_T} + \frac{1}{n_C}\right)}}$$

Where,

 p_T and p_C are the proportions of success for the primary endpoint in the treatment and control groups, respectively, *p* is the pooled estimate of the success rate, and

 n_T and n_C are the sample sizes obtained in the treatment and control groups,

respectively. Two sets of (p, p_T , p_C , n_T , n_C) will be obtained: one at the interim analysis and one at end of the study.

B. Analysis of the Secondary Effectiveness Endpoints

The following describes the analysis techniques to be used for each of the secondary endpoints. To control the family-wise type I error rate at 5%, the Hochberg step-up procedure will be utilized (Hochberg, 1988).

a. FEV₁

Difference between study arms in 'absolute change from baseline' for FEV1 score at 1 year. Descriptive statistics will include means, standard deviations and 95% confidence intervals. An analysis of covariance (ANCOVA) with factor of treatment and baseline FEV1 as a covariate will be used to test the difference between treatment arms. P-value will be adjusted for multiple imputation.

b. 6-Minute Walk Distance (6MWD)

Difference between study arms in 'absolute change from baseline' for 6MWD at 1 year. Descriptive statistics will include means, standard deviations and 95% confidence intervals. An analysis of covariance (ANCOVA) with factor of treatment and baseline 6MWD as a covariate will be used to test the difference between treatment arms. P-value will be adjusted for multiple imputation.

c. St. George's Respiratory Questionnaire (SGRQ)

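### The deciding responder test takes no account of baseline FEV1, although response is defined relative to it; adjusting at the final analysis would bring a modest gain in precision and robustness.

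*Protocol*

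**What the plan says.** - **Endpoint.** Protocol 7.1 compares responder percentages, "as compared to the percentage in the Control arm at 1 year post-procedure". SAP IV.A computes response as percentage change from each participant's own baseline.
- **Deciding test.** SAP IV.A: "The two arms will be compared using the standard normal Z-statistic". The statistic is the pooled two-proportion Z, with boundaries 2.571 (interim) and 2.004 (final). It has no covariate term, and study success rests on this comparison alone.
- **Same measurement, continuous form.** SAP IV.B.a: "An analysis of covariance (ANCOVA) with factor of treatment and baseline FEV1 as a covariate will be used to test the difference". 6MWD and SGRQ are handled in the same way with their own baselines.
- **Randomization.** SAP XI stratifies by site and treated lung, not by baseline FEV1.
- **Section V.** Table 6 lists FEV1 and FEV1 % predicted. They enter a logistic model with treatment only if the arms differ at the two-sided 0.10 level. The stated purpose is to see whether they affect the conclusions; the success rule is unchanged.
- **Interval.** SAP I asks for confidence intervals for continuous variables. For binary ones it says: "Dichotomous variables will be reported as percentages and the numerator and denominator will be reported and defined". SAP IV.A specifies no interval for the primary difference.

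**The concern.** A 15% rule sets a different absolute hurdle for each person. Someone starting at 0.50 L needs 75 mL; someone starting at 1.20 L needs 180 mL. Measurement error in baseline also enters the same ratio. If the change in litres does not scale fully with baseline, low-baseline participants will respond more often in both arms. Leaving baseline out then makes the standard error larger than necessary, and any chance difference in baseline FEV1 stays in the observed responder difference.

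The SAP accepts this reasoning for the continuous FEV1 change but does not apply it to the test that decides the trial. The value is already collected on everyone. At stake are some precision and some protection against a chance imbalance, not the validity of the test.

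**Working it through.** **1. Reproduce the plan's figure.** Inputs are from Protocol 20.3.1. For EBV: "the responder rate in the EBV Study Treatment Group is expected to be approximately 35% at 1 year". Controls are put at 10% or below, power at 90%, alpha at 0.05 two-sided, with 2:1 allocation. The pooled rate is (0.10 + 2×0.35)/3 = 0.2667.
- Uncorrected control n = [1.960√(1.5×0.2667×0.7333) + 1.2816√(0.09 + 0.2275/2)]² / 0.25² = (1.0615 + 0.5785)²/0.0625 = 43.03, rounded up to 44 (132 in total).
- Continuity-corrected n = (43.03/4)[1 + √(1 + 6/(2×43.03×0.25))]² = 48.8, rounded up to 49 control + 98 EBV = **147**, as stated.
- Exact power of the planned Z at 98 v 49 is 94.2% at 1.96 and 93.5% at 2.004.

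**2. Spread of the hurdle.** Baseline eligibility is FEV1 15-45% of predicted. The required gain runs from 0.15×15 = 2.25 to 0.15×45 = 6.75 points of predicted, a three-fold range.

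**3. Does baseline predict response?** The documents give no association, so this is assumed. In an illustrative model (median baseline 0.72 L, log-SD 0.30), change additive in litres gives an odds ratio of about 1.6 per SD lower baseline. Change fully proportional to baseline gives about 1.0.

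**4. Gain at 147 (98 v 49; 4,000 simulated trials each; both tests at 1.96).**

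| Assumed odds ratio per SD lower baseline | 1.0 | 1.5 | 2.0 | 3.0 |
|---|---|---|---|---|
| Power, unadjusted (%) | 93.8 | 94.2 | 94.5 | 94.4 |
| Power, adjusted (%) | 94.4 | 95.3 | 96.5 | 97.4 |
| Variance, unadjusted/adjusted | 1.00 | 1.02 | 1.05 | 1.13 |

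The 0.6-point difference at odds ratio 1.0 comes from using a likelihood-ratio test, not from baseline. A ratio of 1.13 is a cut of 1 − 1/1.13, about 12%, but odds ratio 3.0 is well above the 1.6 in step 3.

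**5. Gain at 190 enrolled.** A 2:1 split gives about 127 v 63.
- Litre-scale simulation (assumed baseline mean 0.75 L, SD 0.20-0.25; measurement SD 0.04-0.10 L; true change SD 0.08-0.12 L, independent of baseline; rates set to 10% and 35%): adjusted/unadjusted variance ratio 0.919-0.969, a cut of 3-8%. This equals 190/0.969 − 190 = 6 to 190/0.919 − 190 = 17 participants. A rerun at five settings gave 0.910-0.957.
- True change proportional to baseline but measurement error in litres: 0.900-0.990.
- Odds ratio 1.6 per SD: about a 2% variance cut and under 1 point of power.

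**6. Chance imbalance.** With assumed SD 0.20-0.25 L, the SE of the baseline difference is SD×√(1/127 + 1/63) = 0.031-0.039 L. The 0.10 trigger fires at 1.645 SE, that is 0.051-0.063 L, so a 0.05 L imbalance escapes it. With EBV 0.05 L lower, the simulated difference is 25.8-26.3 points instead of 25. The SE of the difference is √(0.35×0.65/127 + 0.10×0.90/63) = 5.7 points, so the shift is 0.14-0.23 SE.

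**7. Can a model carry the interim?** At 74 participants (about 49 v 25), expected control responders are 25×0.10 = 2.5, and the chance of none is 0.9²⁵ = 7%. In simulation the logistic model failed to fit in about 7-8% of runs at the design rates. At a common 20% rate, the standardized difference over its robust SE crossed 2.571 in about 1.5-1.8% of runs, against the allotted 1.015%.

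**8. Can it carry the final analysis?** The model fitted almost always. Against 2.004 (nominal 4.511% in Table 2), the standardized statistic rejected in 4.7-5.3% of null runs and the adjusted score test in 4.2-4.6%.

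**9. Mixing the two statistics.** With bounds 2.57057 and 2.00360, the bivariate normal gives overall alpha 0.0500 at correlation √0.5 = 0.707. If the final statistic has 10% less variance, the correlation is √(0.5×0.9) = 0.671 and overall alpha is 0.0506.

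**The case against.** The strongest reply is that nothing is broken. Randomization keeps the unadjusted test valid; in null simulations (20% in both arms) it rejected in 4.7-5.7% of runs, which is within simulation error of 5%. Power is already high and more people were enrolled than planned. The sample size was derived for exactly this test. All of that stands.

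It is also fair to say that baseline FEV1 is not ignored. It is the denominator of the response definition, it is in Table 6, and SAP II makes any dissimilar variable a potential covariate. This stands too, but none of it conditions the deciding test, and a supportive model that appears only after a significance test on baseline is a weak safeguard. Larger imbalances would trigger that model; the 0.05 L example would not, though its effect is small.

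A further reply is that any gain vanishes if change scales with baseline. That holds only when measurement error scales too, or is small (step 5). Which case applies cannot be settled from the documents.

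Finally, replacing the test at both looks would do harm at the interim. Step 7 supports that, and the fix below respects it.

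**Conclusion.** The point holds as a modest matter of efficiency and robustness. The success-defining test omits a baseline value that defines response and that the SAP uses for the continuous form of the same measurement. The likely gain is roughly 0-10% less variance, near zero if both change and measurement error scale with baseline, plus removal of about a 1-point shift from a 0.05 L imbalance. These figures rest on assumed baseline spread, measurement error and change distributions.

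Four stronger readings might be inferred, and the documents support none of them:
- **Inflated type I error or too small a sample.** The 147 reproduces and the planned test holds its level.
- **A plan that ignores baseline FEV1.** Table 6 and the response definition both use it.
- **Baseline FEV1 as an established strong predictor of response.** No association is reported.
- **SAP I barring intervals for binary outcomes.** It merely does not ask for them; SAP VII and the device malfunction section give exact intervals for rates. The missing interval for the primary difference is a separate, smaller omission that the same edit can repair.

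**What to change.** Amend SAP IV.A as follows.

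1. **Interim:** keep the pooled Z and the 2.571 boundary.
2. **Final, specified before unblinding:** in each imputed dataset, fit a logistic regression of response on treatment and continuous baseline post-bronchodilator FEV1, unconditionally. Test treatment against 2.004 with either the covariate-adjusted score test or the standardized risk difference over its robust SE, and name one. Step 8 favors the score test on level. The standardized difference pools more directly over the 20 imputed datasets in SAP IX; a score test needs its pooling rule written down.
3. **Report** the standardized risk difference with an interval matching the final boundary: 1 − 0.04511 = 95.49%.
4. **Fallback:** the pooled Z if the model does not fit. Otherwise keep it as a sensitivity analysis.
5. **If comparative results have already been seen:** leave the Z as primary. Make the baseline-adjusted analysis a fixed, unconditional sensitivity analysis, in place of the 0.10 trigger for baseline FEV1 in SAP V. The timing matters because the SAP revision postdates full enrollment.

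The cost is SAP wording and a little more analysis work, with no new data. If baseline turns out not to predict response, the loss of precision is very small.

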7.2 Safety Endpoint

Evaluation of the short- and long-term adverse events profile of the EBV Treatment arm during the treatment period, defined as the day of the study procedure until 45 days after the study procedure (short), and in the post-treatment period, defined as 46 days after the study procedure until the 1-year follow-up visit (long).

7.3 Secondary Effectiveness Measures

Secondary effectiveness measures will consist of the following:

- 1) Treatment Lobe Volume Reduction (TLVR) for the EBV Treatment Arm
 - i. TLVR, measured as the 'absolute change from baseline' for treated lobe volume as seen via HRCT, will be evaluated at 45 days and 1 year.
 - ii. TLVR, measured as the 'percentage change from baseline' for treated lobe volume as seen via HRCT, will be evaluated at 45 days and 1 year.
- 2) St. George's Respiratory Questionnaire (SGRQ)
 - i. Difference between study arms in 'absolute change from baseline' for SGRQ score at 1 year.
- 3) FEV₁
 - i. Persistence of treatment effect will be evaluated by determining the difference between study arms for 'absolute change from baseline' for FEV₁ at 45 days, 6 months, and 1 year.
 - ii. Persistence of treatment effect will be evaluated by determining the difference between study arms for 'percentage change from baseline' for FEV₁ at 45 days, 6 months, and 1 year.
- 4) 6-Minute Walk Distance
 - i. Difference between study arms in 'absolute change from baseline' for 6MWD at 1 year.
 - ii. Difference between study arms in 'percentage change from baseline' for 6MWD at 1 year.

7.4 Additional Measures

Mean changes and/or changes measured using responder analyses for:

- Spirometry, including FEV₁, forced vital capacity (FVC) and the ratio of FEV₁/FVC
- Body plethysmography, including residual volume (RV), inspiratory capacity (IC), functional residual capacity (FRC), total lung capacity (TLC), and the ratios of RV/TLC and IC/TLC
- SGRQ global and domain (i.e. 'symptoms', 'activity' and 'impacts on daily life') score
- Modified Medical Research Council (mMRC) dyspnea scale score
- BODE Index
- Transitional Dyspnea Index (TDI) from Baseline Dyspnea Index (BDI)

- COPD Assessment Test (CAT)
- SF-36 Health Survey
- EQ-5D Health Survey
- Health Care Utilization Questionnaire
- 6 minute walk distance
- Borg scale dyspnea scores before and after 6MWD test
- Change in use of 'maintenance' medications, including bronchodilators, corticosteroids, antibiotics, and anti-inflammatories
- Daily diary (EXACT-PRO, pulmonary rehabilitation compliance, health status changes)
- Carbon Monoxide Diffusing Capacity (DL_{CO})
- Lung radiographic features
- Blood chemistry measures

7.5 Crossover of Control Study Participants

After completing the 1-year visit, a control arm participant may be permitted to crossover to the study treatment if (s)he continues to qualify for the study treatment. In order to qualify for crossover, a control arm participant must have been followed up successfully through 1 year and demonstrate lack of a clinically important response. The crossover procedure must be scheduled to occur within the 60 days after the 1 year visit. After treatment, the follow-up visits and testing at each visit will be identical to the study schedule for treatment arm participants.

Note: Per Revision H of this protocol, the requirement of a heterogeneity score of 15% between lobes is not applicable for any remaining crossover subjects. The most diseased target can be treated regardless of heterogeneity, provided that the target lobe is collateral ventilation negative (CV-).

Patients treated after approval of this Amendment will fall outside of the original 60 day window from the 1-year visit date. This delay will not be marked as a deviation from the protocol.

7.6 Interim Analysis

An interim data analysis designed to evaluate effectiveness for continuing crossover of Control arm study participants after the 1 year follow-up visit to EBV treatment will be performed when 74 (50% of the required minimum of 147) study participants have completed the 1 year follow-up. If crossover of Control arm study participants is found to be justified by the interim analysis then crossover of Control arm study participants after (s)he has reached the 1-year time point may be continued. The results of the interim analysis will be reviewed by the DSMB and FDA. If the DSMB recommends not continuing crossing control arm participants to EBV treatment, then those control arm participants who have not crossed over will exit from the study protocol after the 1-year visit.

7.7 Long-Term Follow-Up

Data will be collected annually through 5 years for study participants receiving the study treatment. Per the regulatory plan agreed to with FDA, 1 year of follow-up is required pre-approval and the remaining 4 years of follow-up will be conducted post-approval. The annual 2-, 3-, 4-, and 5-year follow-up data will consist of FEV₁ and adverse events.

8.0 STUDY PARTICIPANT MANAGEMENT

8.1 Clinical Site Study Team

The Principal Investigator at each clinical site will be responsible for identifying and providing oversight of the study team at the clinical site. The clinical site study team will be responsible for executing all study-related activities.

8.2 Clinical Study Site Training

Prior to enrolling any study participants, the site Principal Investigator(s) and the Study Coordinator(s) will complete the Pulmonx Clinical Study Training Program. An overview of the training program is provided in Section 18.0.

